3.2 Exclusion criteria

Patients should not enter the study if any of the following exclusion criteria are fulfilled:

1. Involvement in the planning and/or conduct of the study (applies to both AstraZeneca staff and/or staff at the study site).
2. Participation in another clinical study with an investigational product during the last 21 days.
3. Any chemotherapy within 3 weeks of the first dose of AZD1775.
4. Use of anti-cancer treatment drug ≤ 21 days or 5 half-lives (whichever is shorter) prior to the first dose of AZD1775. For study drugs for which 5 half-lives is ≤ 21 days, a minimum of 10 days between termination of the study drug and administration of AZD1775 treatment is required.
5. Major surgical procedures ≤ 28 days of beginning study treatment, or minor surgical procedures ≤ 7 days. No waiting required following port-a-cath placement or central nervous access placement.
6. Grade >1 toxicity from prior therapy (except alopecia or anorexia).
7. No other anti-cancer therapy (chemotherapy, immunotherapy, hormonal anti-cancer therapy, radiotherapy [except for palliative local radiotherapy]), biological therapy or other novel agent is to be permitted while the patient is receiving study medication. Patients on LHRH analogue treatment for more than 6 months are allowed entry into the study and may continue at the discretion of the Investigator.
8. Patient has an inability to swallow oral medications. Note: Patient may not have a percutaneous endoscopic gastrostomy (PEG) tube or be receiving total parenteral nutrition (TPN).
9. Known malignant central nervous system (CNS) disease other than neurologically stable, treated brain metastases – defined as metastasis having no evidence of progression or haemorrhage for at least 2 weeks after treatment. Must be off any systemic corticosteroids for the treatment of brain metastases at least 14 days prior to enrolment.

10. Patient has had prescription or non-prescription drugs or other products known to be sensitive CYP3A4 substrates or CYP3A4 substrates with a narrow therapeutic index, or to be moderate to strong inhibitors/inducers of CYP3A4 which cannot be discontinued two weeks prior to Day 1 of dosing and withheld throughout the study until 2 weeks after the last dose of study drug. The use of sensitive substrates of CYP3A4, such as atorvastatin, simvastatin and lovastatin is also prohibited in this study. Co-administration of aprepitant or fosaprepitant during this study is prohibited (see Section 7.8.3 and Appendix G).
11. Caution should be exercised when inhibitor or substrates of P-glycoprotein (P-gp), substrates of CYP1A2 with a narrow therapeutic range, sensitive substrates of CYP2C19 or CYP2C19 substrates with a narrow therapeutic range are administered with AZD1775.
 - Transporter studies (in vitro) have shown that AZD1775 is an inhibitor of breast cancer resistance protein (BCRP). Please refer to Appendix G for use with BCRP substrates.
 - Herbal preparation are not allowed throughout the study. These herbal medications include but are not limited to St. John's wort, kava, ephedra (mahung), ginkgo biloba, dehydroepiandrosterone (DHEA), yohimbe, saw palmetto and ginseng. Patients should stop using these herbal medications 7 days prior to the first dose of study treatment.
12. Any known hypersensitivity or contraindication to the components of the study drug AZD1775.
13. Any of the following cardiac diseases currently or within the last 6 months as defined by New York Heart Association (NYHA) \geq Class 2 (see Appendix E)
 - Unstable angina pectoris
 - Congestive heart failure
 - Acute myocardial infarction
 - Conduction abnormality not controlled with pacemaker or medication
 - Significant ventricular or supraventricular arrhythmias (patients with chronic rate-controlled atrial fibrillation in the absence of other cardiac abnormalities are eligible).
14. Patients with mean resting corrected QT interval (specifically QTC calculated using the Fridericia formula [QTcF]) \geq 450 msec for males and \geq 470 msec for females from 3 electrocardiograms (ECGs) performed within 2-5 minutes apart at study entry or congenital long QT syndrome (see Section 5.2.4). In addition, Part A safety lead-in patients must have baseline triplicate ECGs and the Part B patients will have an ECG collected at baseline and triplicate ECGs if clinically indicated.

Triplicate ECGs will be obtained with PK collections as presented in the Study Plan tables.

15. Pregnant or lactating women.
16. Serious active infection at the time of enrolment, or another serious underlying medical condition that would impair the ability of the patient to receive study treatment.
17. Presence of other known active invasive cancers.
18. Psychological, familial, sociological, or geographical conditions that do not permit compliance with the protocol.
19. Previous enrolment in the present study.

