- c Vital signs (resting heart rate, blood pressure, temperature and weight) at the Screening visit will include height. After Screening, height will not be measured. Vital signs and weight will be obtained prior to study drug administration according to institutional practice, end of treatment (EOT) visit, PFS follow-up assessment, and the final protocol visit (FPV).

- d Clinical chemistry will include measurements of glucose, BUN, creatinine, sodium, potassium, chloride, total calcium, CO₂, alkaline phosphatase (ALP), AST, ALT, total bilirubin, total protein, and albumin.
- e Coagulation performed at baseline only (PT or INR with PTT). Repeat at the beginning of every cycle if patient on Coumadin.
- f An ECG will be collected at baseline to confirm eligibility (see Section 3.2). Cycle 1 Day 1 pre-dosing triplicate 12-lead ECGs will be collected within approximately 2-5 minutes intervals to determine the mean resting corrected QTc using the Fridericia formula (QTcF) <470 msec for females and <450 for males if clinically indicated. Thereafter, patients will have an ECG only as clinically indicated. Repeated ECGs should be performed on the same equipment if possible.
- g Pregnancy tests will only be performed in women of childbearing potential 3 days prior to first dose of study treatment. This will be repeated at the beginning of each treatment cycle. the EOT visit. and at the FPV (see Section 5.2.6).
- h Patients will be restaged after every 2 cycles (every 6 weeks [± 7 days]). Patients with progressive disease or unacceptable toxicity should be discontinued from the study treatment; patients with SD or response to therapy will continue treatment. Tumour status will be compared to baseline and confirmation of response will be evaluated by physical examination, anatomic imaging measurement, and performance status
- i CT scans/MRIs of the chest and abdomen and pelvis are required at baseline and every 2 cycles (6 weeks).
- j The same method of assessment and the same technique must be used to characterize each identified and reported lesion at baseline and during subsequent imaging procedures. Patients continuing study treatment for a minimum of 1 year may have the tumour imaging assessments expanded to every 4 cycles (12 weeks [± 7 days]).
- k Patients without evidence of undue toxicity may continue treatment with study drugs until disease progression occurs as long as they are achieving clinical benefit and desire to continue therapy.

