- o Blood PK samples will be collected from consenting patients pre-dose and 2-4 hours post dose on Cycle 1 Day 3 or Day 10, Cycle 2 Day 3 or Day 10 and Cycle 4 and beyond every 2 cycles Day 3 or Day 10. These samples may become optional once there are samples from 40-50 patients (at least 10 patients from each expansion cohort). Patients will also have 12-lead ECGs obtained after the patient has been resting semi-supine position for 10 minutes before the PK sample collection. For each time point three ECG recordings should be taken at approximately 2-5 minute intervals. Details for processing, handling, and shipping are in the Laboratory Manual.
- p Intentionally Blank

- q ctDNA and cytokine plasma samples will be collected pre-dose Cycle 1 Day 1, Cycle 1 Day 15, and pre-dose on Cycle 2 Day 1, Cycle 2 Day 8, 2-4 hours after dosing, pre-dose on Cycle 4 Day 1 and Cycle 6 Day 1, thereafter Day 1 every 2 cycles (about 6 weeks) and at the time of disease progression (see Section 5.6.1). Patients continuing study treatment for a minimum of 1 year may have the ctDNA and cytokine collection expanded to every 4 cycles (12 weeks [± 7 days]). Patients continuing treatment after FPV will have a ctDNA sample collected at the time of progression. Details for processing, handling, and shipping are in the Laboratory Manual.
- r A whole blood sample will be collected from ovarian patients only for immune profiling flow cytometry at baseline (within 2 weeks of initiation of dosing), pre-dose Cycle 1 Day 1, Cycle 1 Day 15, Cycle 2 Day 1 pre-dose, Cycle 2 Day 8, 2-4 hours after first dose of the day, and Cycle 4 Day 1 pre-dose (see Section 5.6.2). Details for processing, handling, and shipping are in the Laboratory Manual.
- s Optional whole blood PGx samples (10 mL) will be taken pre-dose on Cycle 1 Day 1 (see Section 5.6.5). If for any reason the sample is not drawn at Cycle 1 Day 1, it may be taken at any visit until the last study visit. Only one sample should be collected per subject for genetics during the study. This sample is **optional** and must be taken from patients who have provided informed consent for genetic sampling and analysis.

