5.2.4 Electrocardiograms

All patients must have a screening 12-lead safety electrocardiogram (ECG) (paper ECG printout of 10 seconds for Investigator review) in order to meet eligibility criteria (see Section 3.2).

The patients in the Part A Safety Lead-in will have triplicate ECGs collected at each PK collection time point (see Table 1). Triplicate ECGs will be collected in Part B patients at baseline if clinically indicated (see Table 2).

Triplicate ECG recordings should be taken within an approximate 5-minute period. Additional ECGs may be taken at any other time the Investigator deems necessary for safety during the administration period. Twelve-lead ECGs will be obtained after the patient has been resting semi-supine for at least 10 minutes before the start of each recording and they must be in the same supine body position (maximum 30 degrees flexion in the hip and feet not in contact with the footboard) at the recording time point; except for the baseline ECG following the administration of AZD1775. For each time point during the PK collections for Part A, 3 ECG recordings should be taken at approximately 2-5 minutes interval. The mean QTcF interval for all 3 ECGs must be ≤ 450 msec for male patients and ≤ 470 msec for female patients prior to the initiation of treatment. A standardised ECG machine should be used and the patient should be examined using the same machine throughout the study if possible.

Part A - ECGs will be obtained before the PK blood collection as follows: Screening, Cycle 1 Day 1 and on Cycle 1 Day 3 or Day 10. ECG collected from time (h) post AZD1775 dose: pre-dose, 1h, 2, 4, 6, 8 and 12h post dose. Repeated ECGs should be performed on the same equipment if possible.

Part B - Patients will have ECGs performed at screening and baseline as indicated in the Study Plan detailed in Table 2. Patients consenting to the PK blood collections will have ECGs performed before the PK collection pre-dose and at 2-4 hours post dose as outlined in Table 2 and repeated only if clinically indicated.

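### Exclusion criterion 14 is defined on the mean QTcF of three entry ECGs, but the Part B schedule requires only one

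*Protocol*

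**What the plan says.** **Section 3.2, criterion 14, first sentence.** A patient is excluded if mean resting QTcF is ≥ 450 ms (men) or ≥ 470 ms (women), the mean being taken "from 3 electrocardiograms (ECGs) performed within 2-5 minutes apart at study entry". Nothing limits this to Part A. The opening of Section 3 allows no exception to the eligibility criteria.

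**Section 3.2, criterion 14, continuation.** Part A patients must have baseline triplicates, whereas "the Part B patients will have an ECG collected at baseline and triplicate ECGs if clinically indicated".

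**Table 2 (Part B), footnote f.** "An ECG will be collected at baseline to confirm eligibility", with a reference back to Section 3.2. The Cycle 1 Day 1 pre-dose triplicate is then described as determining the mean QTc "using the Fridericia formula (QTcF) <470 msec for females and <450 for males if clinically indicated". Table 1 footnote f (Part A) has almost the same sentence without the closing condition. Table 2 footnote b waives the Cycle 1 Day 1 ECG if the screening ECG falls within 3 days before treatment.

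**Section 5.2.4.** "Triplicate ECGs will be collected in Part B patients at baseline if clinically indicated". A later sentence begins "The mean QTcF interval for all 3 ECGs must be" and gives the limits as ≤ 450 ms (men) and ≤ 470 ms (women) before treatment starts.

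**Table 2, footnote o.** At PK visits, on Day 3 or Day 10 of a cycle, "For each time point three ECG recordings should be taken at approximately 2-5 minute intervals".

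**The concern.** The exclusion is defined on a quantity that the Part B schedule does not reliably produce. A site working from criterion 14 takes three recordings at entry. A site working from Table 2 takes one and adds a triplicate only if it sees a clinical reason. Both can say that they followed the protocol, so the same safety exclusion can be applied differently across sites.

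Section 1.3.2 lists QTc prolongation as an adverse drug reaction of AZD1775 monotherapy, so this is not a formality. The pre-dose value also matters later. It is the natural reference for the Table 9 row that stops treatment on a shift of ≥ 60 ms, and for the Part B secondary objective on QTc (Section 2.2).

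**Working it through.** **1. Is there an unconditional pre-dose triplicate for Part B?**

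| Place | Part A | Part B |
|---|---|---|
| Criterion 14, first sentence | mean of 3 at entry | mean of 3 at entry |
| Criterion 14, continuation | triplicate at baseline | one ECG; triplicate if indicated |
| Footnote f (Table 1 / Table 2) | Cycle 1 Day 1 triplicate | Cycle 1 Day 1 triplicate if indicated |
| 5.2.4, baseline | triplicates at each PK time point, including Day 1 pre-dose | triplicate if indicated |
| Triplicates at PK visits | from Cycle 1 Day 1 | from Cycle 1 Day 3 or Day 10 |

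Only the first row obliges a Part B site to record three ECGs before dosing, and no schedule entry implements it. The PK-visit triplicates come after dosing has begun, so they cannot serve eligibility.

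**2. How many patients are under this schedule?** Section 8.1 gives 12 patients in Part A and 60 ovarian, 50 TNBC and 50 SCLC patients in Part B. 60 + 50 + 50 = 160 and 160 + 12 = 172, which reproduces the plan's total. The Part B share is 160/172 = 93.0%. Without the 20 optional patients in each of TNBC and SCLC it is 120/132 = 90.9%.

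**3. What does one ECG instead of three do at the limit?** The protocol gives no replicate SD. Assume s = 6 to 12 ms with independent normal errors. For a patient whose underlying QTcF is d ms above the limit, the chance of reading below it is Φ(−d/s) on one ECG and Φ(−d√3/s) on the mean of three.

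| d | s | one ECG | mean of three |
|---|---|---|---|
| 5 ms | 6 ms | 0.202 | 0.074 |
| 5 ms | 12 ms | 0.338 | 0.235 |
| 10 ms | 6 ms | 0.048 | 0.002 |
| 10 ms | 12 ms | 0.202 | 0.074 |

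By symmetry, the same figures are the chances of wrongly excluding a patient d ms below the limit.

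**4. Does it disturb the 60 ms stopping row in Table 9?** Take the largest SD, s = 12 ms, and add an assumed occasion-to-occasion SD of 10 ms at both times. Let the on-treatment value be a mean of three.
- Single baseline: √(2·10² + 12²·(1 + 1/3)) = √392 = 19.8 ms, so 60 ms lies 60/19.8 = 3.0 SD from no shift.
- Triplicate baseline: √(2·10² + 12²·(1/3 + 1/3)) = √296 = 17.2 ms, so 60 ms lies 60/17.2 = 3.5 SD from no shift.

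A false trigger from noise is rare either way, about 0.1% with the single baseline. The comparison of a single baseline with an on-treatment triplicate arises only in Part B patients who give PK samples. Section 5.3.2 requires sampling at about 3 to 5 sites, aims for at least 50 patients, and recommends it elsewhere.

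**5. The printed limits.** At a mean of exactly 450 ms (men) or 470 ms (women), criterion 14 excludes, footnote f does not admit, and 5.2.4 admits. Table 9 holds drug from those same values.

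**The case against.** The best reply is that the second sentence of criterion 14 opens with *In addition*. On that reading the first sentence sets a three-ECG entry test for everyone, and the rest adds separate baseline recordings. Section 5.2.4 does speak of Part B ECGs at both screening and baseline. A site that takes three recordings at entry breaches none of these texts. This is a fair reading and may be what was meant. It does not close the gap, because Table 2 does not schedule that entry triplicate and footnote f ties eligibility to one ECG plus a conditional triplicate. Two single recordings, at screening and on Day 1, are not the mean of three taken minutes apart, and footnote b can waive the second.

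Three narrower objections stand. The sentence in 5.2.4 on the mean of all three ECGs directly follows one about Part A PK time points and may concern Part A only; the conflict does not depend on it. Table 1 footnote f also opens with a single ECG to confirm eligibility, so that phrase alone proves little; what distinguishes Part B is the added clinical-indication condition. And Version 5 introduces the Final Protocol Visit and refers to a primary data cut-off. This suggests a late stage, so there may be few new patients to screen, although the protocol does not say that Part B enrolment has closed.

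**Conclusion.** The inconsistency is real. Criterion 14 requires a three-ECG mean from every patient, and the Part B schedule makes the pre-dose triplicate conditional. This rests on the text alone. The misadmission probabilities rest on the assumed SD of 6 to 12 ms and apply only to a patient close to the limit; they give no count of patients.

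Two stronger readings are tempting and are not supported. A reader might infer that 93% of patients were, or would be, enrolled without a valid QTcF check. That percentage is the share of maximum planned enrolment under the ambiguous schedule; sites may have taken triplicates, and the documents do not show what was done. A reader might also infer that a single baseline undermines the 60 ms stopping row or the QTc objective throughout Part B. The mismatch is confined to patients who give PK samples, and its effect on the 60 ms row is negligible even at the largest assumed SDs.

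The difference between ≤ and < in 5.2.4 is a genuine slip that matters only at exactly 450 or 470 ms. The primary endpoints are untouched. Severity is minor to moderate: a safety exclusion should have one operational definition.

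**What to change.** Preferred: remove the clinical-indication condition from the Part B pre-dose triplicate in criterion 14, Section 5.2.4 and Table 2 footnote f. State that the mean QTcF of those three recordings decides eligibility and is the baseline for Table 9.

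Alternative: if one ECG is intended for Part B, rewrite the first sentence of criterion 14 to say so, state when triplicates are required, and limit the three-ECG sentence in 5.2.4 to Part A.

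In either case, change 5.2.4 to < 450 ms for men and < 470 ms for women, to agree with criterion 14, footnote f and the Table 9 hold band. For Part B patients already treated, list how many ECGs each baseline QTcF rests on, so that shifts can be read accordingly.

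The cost is wording in three places and two further recordings, a few minutes apart, for each newly enrolled Part B patient. Criterion 14 already calls for those recordings. The sample size does not change.

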3.3 Subject enrolment

Investigator(s) should keep a record, the subject screening log, of subjects who entered pre-study screening.

The Principal Investigator (PI) at each site will:

Obtain a signed ICF from the potential patient before any study specific procedures are performed. Obtain study identifier according to the instructions provided in the Study Reference Manual.

For inclusion in i) the optional exploratory genetic research and ii) the optional tumour biopsy, patients must fulfil the following criteria:

- Provision of informed consent for genetic research
- Provision of informed consent for optional tumour biopsies

Exclusion from this genetic research may be for any of the exclusion criteria specified in the main study, or for any of the following:

- Previous allogenic bone marrow transplant
- Non-leukocyte depleted whole blood transfusion in 120 days of genetic sample collection

If a patient declines to participate in the optional exploratory genetic research or the optional tumour biopsies, there will be no penalty or loss of benefit to the patient. The patient will not be excluded from other aspects of the study.

- Assign potential subject a unique enrolment number
- A sufficient quantity of archival or recent tumour tissue samples must be available to enrol into an expansion cohort (Part B). Molecular profile assessments may be performed on archived or fresh tumour tissue taken for routine clinical purposes if archived tissues are unavailable.

All tumour samples will be analysed for a range of cancer-related genes such that clinical response can be correlated to the gene aberrations.

BRCA wild-type is defined as no evidence of deleterious or suspected deleterious mutation in *BRCA1* or *BRCA2* genes. *BRCA1* and/or *BRCA2* variants that are classified as ‘Variants of uncertain clinical significance’ or ‘Variant of unknown significance (VUS)’ are eligible, as well as ‘Variant, favour polymorphism’ or ‘benign polymorphism’.

TNBC and SCLC biomarker ‘positive’ cohorts to be analysed include amplifications in *CCNE1*, *MYC*, *MYCL1* or *MYCN*.

Biomarker ‘positive’ TNBC and SCLC cohorts are defined as amplifications in *CCNE1*, *MYC*, *MYCL1*, or *MYCN*. Biomarker ‘negative’ TNBC and SCLC cohorts are defined as the absence of the qualifying amplification (as specified in Sections 3.2, 5.4.3, and 7.2.2).

Patients may not have to wait for confirmation of the pathology QC check if molecular analysis results are already available to confirm the specific biomarker of interest (i.e., *BRCA1* or *BRCA2* genes in ovarian cancer, amplification of at least one of the following genes: *CCNE1*, *MYC*, *MYCL* or *MYCN* in TNBC or SCLC). The results must be from a certified laboratory and approved by the Sponsor or designee on a case-by-case basis. However, submission of archived or fresh tumour tissue to the Central Laboratory is required for analysis (see Laboratory Manual). Patients with previous genetic profile testing results from a Sponsor approved certified laboratory tumour samples are considered insufficient by the pathology QC check will be allowed to remain on-study.

Determine patient eligibility. See Sections 3.1 and 3.2

If a subject withdraws from participation in the study, then his/her enrolment code cannot be reused.

Human protection committee/Institutional Review Board (IRB) approval of this protocol and associated consent form(s) is required before any patient may be enrolled into the study.

3.4 Procedures for handling incorrectly enrolled patients

Patients who fail to meet the eligibility criteria should not, under any circumstances, receive study medication. There can be no exceptions to this rule. Patients who are enrolled but

subsequently found not to meet all the eligibility criteria must not be initiated on treatment and must be withdrawn from the study.

When a patient does not meet all the eligibility criteria but is incorrectly started on treatment, the Investigator should inform the Medical Monitor immediately and a discussion should occur between the Medical Monitor and the Investigator regarding whether to continue or discontinue the patient from treatment. The Medical Monitor must ensure all decisions are appropriately documented.

